6.2 Summary of findings from non-clinical studies

Not applicable, as this research cannot have been carried out in non-clinical settings.

6.3 Summary of findings from clinical studies

Not applicable.

6.4 Summary of known and potential risks and benefits

Patients will have to measure their weight, temperature, blood pressure and heart rhythm on a regular basis. Regularly, they also will be asked questions about their general health. These activities may take some of their time.

A potential risk is that patients may be incorrectly assured that their data is monitored all the time by a trained physician. This might give them a false sense of security and hold them back from seeking medical assistance when this is required. To prevent this, we will

very clearly state in the patient information form (PIF) that this is not the case, and will make this integral part of the explanation when a patient starts with The Box.

A second potential risk is that patients may become alarmed by an incorrect detection of atrial fibrillation by the Withings Move ECG. Since it is not CE marked for AF detection, and given the results from a current validation study, we cannot exclude the occurrence of false positives or negatives. The smart watch and associated app give a warning when the measurement shows irregularities. It then either results in an “inconclusive” measurement or detects “atrial fibrillation”. It has been shown that this occurs when there are small irregularities in the hearth rhythm, such as atrial or ventricular extrasystoles or short pauses . The device then usually results in “inconclusive” but can also show “atrial fibrillation”. This can hence (incorrectly) distress the patient and cause him/her to seek unnecessary medical help. We will remedy this by clearly instructing the patient with what to do and who to contact in case of suspected AF.

After a measurement the Withings Move ECG performs a standard analysis resulting in either “normal”, “inconclusive” or “atrial fibrillation”. If their ECG smartwatch shows “atrial fibrillation” they are instructed to contact a dedicated nurse specialist who will check the measurements and refer them to the cardiology outpatient clinic if necessary. If the result is “inconclusive”, the patient is asked to repeat the measurement the next day. When the repeated measurement shows “inconclusive” again or when the measurement shows a warning for potential AF, they are instructed to also contact the dedicated nurse specialist who will contact the patient for further follow-up if necessary.

All devices used by patients for personal management in this study are CE marked, non-invasive, easy-to-use and electrically safe within their intended use. Using the devices is with very limited risks.

This study has multiple potential benefits for the patients: First, patients can measure their own blood pressure, weight, activity, and heart rhythm, which can reassure patients and give them more insight in their own health (the so-called ‘patient empowerment’). Furthermore, this data gives the doctor more insight in the health status of patients, potentially leading to better hypertension management and earlier detection of atrial fibrillation.

6.5 Description and justification of route of administration and dosage

Not applicable.

6.6 Dosages, dosage modifications and method of administration

Not applicable.

6.7 Preparation and labelling of Investigational Medicinal Product

Not applicable.

6.8 Drug accountability

Not applicable.

7. NON-INVESTIGATIONAL PRODUCT

Not applicable.

8. METHODS

8.1 Study parameters/endpoints

8.1.1 Main study parameter/endpoint

The primary objective of this study is the gathering of data on blood pressure management as a basis for power analysis in future trials. This will be evaluated by a before-after-comparison of systolic and diastolic blood pressure in mmHg as measured by the self-measurements with the Stroke Box.

8.1.2 Secondary study parameters/endpoints

The secondary objectives of this study are:

- Gathering data on self-measured heart rhythm from the Withings Move ECG as an indicator of atrial fibrillation, weight and activity of patients using the Stroke Box, and performing a quality assessment of the collected data as assessed by regularity of assessments and frequency of occurrence of measurement error.
- The potential change in self-management of the patients due to the Stroke Box as measured through changes in lifestyle. This will be measured using changes in results from questionnaires on physical activity and healthy lifestyle intentions taken at the start and at the end of the study and the development of weight of the patient.

For the evaluation of physical activity we will adapt the Short Questionnaire to Assess Health enhancing physical activity questionnaire (SQUASH)²⁰, for the evaluation of healthy lifestyle intentions we will use the Healthy Lifestyle Intentions (HLI) questionnaire.

The evaluation of the self-management of the patient will be assessed by the Reach Efficacy Adoption Implementation Maintenance (RE-AIM) model with a mixed model evaluation based on the normalization process theory.²¹⁻²³

- Assessment of the patient adherence to the self-measurements and pharmacotherapeutic prophylactic therapy, using the Partners In Healthcare (PIH) questionnaire which measures how the patient manages his/her own disease. At the end of the study a comparison will be made between the group of patients who used the IkOefenZelf platform and those who did not.
- The technical implementation and patient adherence to the self-measurements by analysing how often they performed the measurements, if they experienced any problems as measured through the questions they asked during the study, and how they experienced the overall implementation as measured through the mHealth App Usability Questionnaire (MAUQ)²⁴ at the end of the study.
- User based evaluation of the technical – and workflow implementation for the GPs using the Stroke Box as evaluated with the Acceptability of Intervention Measure (AIM), Intervention Appropriateness Measure (IAM), and Feasibility of Intervention Measure (FIM)²⁵ questionnaires for healthcare professionals.

8.1.3 Other study parameters

- Age
- Sex
- Body Mass Index
- Cardiovascular risk factors including medication (hypertension, diabetes mellitus, hypercholesterolemia, smoking, alcohol)
- Cardiovascular medical history (atrial fibrillation, stroke including all subtypes, heart failure, myocardial infarction)
- Stroke specific (stroke related disabilities as assessed by the National Institutes of Health Scale Score at discharge, modified Rankin Scale at discharge)
- The GP practice where the patient is registered and how the self-measurements are shared with the GP (i.e. via Medical Dashboard or manually)

8.2 Randomisation, blinding and treatment allocation

This is a non-randomized, non-blinded study.

8.3 Study procedures

For the small prospective cohort for the pilot, patients who are admitted for an ischemic or hemorrhagic stroke in the LUMC will be included in the day or days before dehospitalization and after post-stroke stabilization. After inclusion we will personally contact the GP of the patient to also ask their willingness to collaborate in the pilot. After agreement of their GP, the included patients will receive the Stroke Box with all devices listed under section 6 of this protocol. Patients will be instructed on usage of the devices by a neurology PhD student. Furthermore, for each device a detailed user guide is available on <https://hartlongcentrum.nl/informatie-voor-patienten/the-box/handleidingen/>.

If extra help is necessary, patients will have an e-consult in which a patient does not have to go to the hospital. Instead, he or she will talk with a specialist from the Box-helpdesk who will be able to guide the patient through the self-measurements and provide technical assistance where necessary.

Patients will be asked to measure their weight and blood pressure once a week where they are recommended to do this on the same day and time every week. Additionally, they will be asked to keep track of their activity data (i.e. steps) on a regular basis, which can be monitored continuously by wearing the smartwatch. All

data will be automatically transferred to the LUMC. In order to code the data, patients will receive an anonymous email address, as described earlier in this protocol. Data will be stored on LUMC-owned servers.

The patient's blood pressure measurements and lifestyle data (measured weight and activity) is accessible for the GP through Medical Dashboard. For GPs who do not yet work with Medical Dashboard, the patient will be asked to show his measurements to the GP in the following way during the regular visits. The patient can either show his measurements in the app or make a printout of the data to be shown to the GP or GP nurse.

When the patient records abnormal measurements indicating a high or rapid increase in blood pressure, they are instructed to not immediately contact a physician. This, in order to reduce the amount of (unnecessary) additional consults with the GP. Specifically, the patient is instructed to only contact their GP if they record a systolic blood pressure >140 mmHg for three days in a row or take up immediate contact if they record a systolic blood pressure >180 mmHg which is cause for immediate adjustment of the hypertension medication according to the NHG guidelines.

In addition to the standard care where patients receive a 48-hour Holter, patients who are suspected to have atrial fibrillation because of e.g. a cryptogenic stroke will be asked to also perform home measurements of their heart rhythm on a daily basis. They are recommended to do this on the same day and time every day. They will be very clearly instructed that their ECG measurements are not monitored regularly and that they should contact 112 in case of emergency.

After a measurement the Withings Move ECG performs a standard analysis resulting in either "normal", "inconclusive" or "atrial fibrillation". If their ECG smartwatch shows "atrial fibrillation" they are instructed to contact a dedicated nurse specialist who will check the measurements and refer them to the cardiology outpatient clinic if necessary. If the result is "inconclusive", the patient is asked to repeat the measurement the next day. When the repeated measurement shows "inconclusive" again or when the measurement shows a warning for potential AF, they are instructed to also contact the dedicated nurse specialist who will contact the patient for further follow-up if necessary. It should be noted that a clinical diagnosis will never be based on the self-measurements. Instead they serve as an early screening tool leading to patients with potential AF to be invited to the cardiology outpatient clinic to receive a diagnosis via the standard Holter measurement.

All ECG data are collected after the study and re-inspected by a PhD researcher of the LUMC for AF and in case of doubt checked again by an experienced cardiologist. In case of suspected AF, the patient is invited to the cardiology outpatient clinic. As 87% of stroke patients have ischemic strokes¹⁶ and about a

third of those have cryptogenic strokes, we expect to find cryptogenic strokes in about 29% of the LUMC stroke population.¹⁷

Finally, the first ten patients with a modified Rankin Scale (mRS) ≥ 2 will receive access to the IkOefenZelf platform and will be asked to perform the practice modules on a regular basis.

Patients who smoke will also be asked to install the StopAdvisor app. This app will help them to quit smoking. The app is freely available from the IOS App Store and the Google Play Store.

Questionnaires

At the start and end of the study the patient will receive several questionnaires to evaluate their experiences with self-management, physical activity, healthy lifestyle intentions, their user experience, and their experience with eHealth. To evaluate the change in physical activity and lifestyle of the patient, they will be asked to fill out the SQUASH and HLI questionnaires at the start and end of the study. These questionnaires investigate respectively the amount of physical activity (e.g. sports) a patient has and what their intentions to a healthy lifestyle are (which includes questions on e.g. diet, smoking and alcohol use). In order to evaluate the experience of the patient with the self-management, they will be asked to fill out the PIH questionnaire at the start and the end of the pilot which measures how the patient manages his/her own disease. Finally, to evaluate the patient experience with the overall implementation of the Stroke Box, we will ask them to fill out the MAUQ questionnaire at the end of the study which includes questions on the technical ease-of-use, the general appearance and usefulness of the Stroke Box.

Moreover, we will evaluate the GP experience with the Stroke Box via the AIM, IAM and FIM²⁵ questionnaires for healthcare professionals which are four-item measures of implementation outcomes that are often considered “leading indicators” of implementation success.²⁶ An overview of the questionnaires used is given in the Table below.

Implementation will be assessed by the Reach Efficacy Adoption Implementation Maintenance (RE-AIM) model with a mixed model evaluation based on the normalization process theory.²¹⁻²³ The implementation will be evaluated from the perspective of the neurologists, GPs, practice assistant GP and patients.

Subject	Questionnaire	Estimated time
Physical activity	Short Questionnaire to Assess Health enhancing physical activity questionnaire (SQUASH) ²⁰	5 min
Healthy lifestyle intentions	Healthy lifestyle intentions questionnaire	4 min

Self-management	Partners In Health (PIH) questionnaire ¹⁸	4 min
Patient experience	mHealth App Usability Questionnaire (MAUQ) ²⁴	4 min
GP experience	Acceptability of Intervention Measure (AIM), Intervention Appropriateness Measure (IAM), and Feasibility of Intervention Measure (FIM) ²⁵	3 min

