Objective: The overall aim of this pilot is to evaluate the technical feasibility and clinical implementation of the Stroke Box by evaluating user experience and hypertension management. The primary objective is gathering data on blood pressure management for power calculation for a future randomized clinical trial where the effect of the Stroke Box on hypertension management and AF detection will be studied. The secondary objectives will be gathering and evaluating data on heart rhythm, weight and activity of patients using the Stroke Box, evaluating the technical- and workflow implementation for healthcare professionals, evaluating the self-management and user-experience of patients, assessing the patient adherence to the self-measurements and pharmacotherapeutic prophylactic therapy, and evaluating the correct functioning of the IT infrastructure, hardware and LUMC Care app, and to assess the correct use of all stakeholders involved in the eHealth support and telemonitoring with the Stroke Box.

Study design: This study is a prospective cohort study to evaluate the implementation of the Stroke Box and gather data. For the first 5 patients we will mainly evaluate the technical procedures of the study in addition to the other objectives. For the remainder, we will be gathering data on blood pressure management, patient engagement and have a user-based

evaluation of the eHealth infrastructure during a six-month follow-up period. We will do evaluations of the collected data based on a before-after comparison of blood pressure and questionnaire results.

Study population: Patients admitted for a TIA, ischemic or haemorrhagic stroke in the LUMC. We will include 55 patients in total of which in the first 5 patients we specifically focus on testing and evaluating the technical feasibility.

Intervention (if applicable): The Stroke Box will contain a blood pressure monitor, weighting scale, single-lead ECG wristwatch with activity tracking and associated apps. Patients are asked to measure the associated factors on a weekly basis. In addition, all patients will be asked to fill in a questionnaire at the start and the end of the study. Patients will participate for 6 months in the pilot.

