Main study parameters/endpoints: The primary objective of this study is the gathering of data on blood pressure management as a basis for power analysis in future trials. The secondary objectives will be gathering and evaluating data on heart rhythm, weight and activity of patients, evaluating the technical- and workflow implementation for healthcare professionals, evaluating the self-management and user-experience of patients, assessing the patient adherence to the self-measurements and pharmacotherapeutic prophylactic therapy, and finally evaluating the technical feasibility for all stakeholders.

Nature and extent of the burden and risks associated with participation, benefit and group relatedness: Patients are asked to measure weight, blood pressure and heart rhythm on a weekly basis, which takes approximately 5-10 minutes. All devices used by patients for personal management in this study are non-invasive, easy-to-use, CE marked and electrically safe within their intended use. Using the devices comes with very limited risks. This study has several potential benefits for patients. First, patients can measure their own blood pressure, heart rhythm and weight, which can give them more insight in their own health and may spark a healthier lifestyle (the so-called 'patient empowerment'). Furthermore, these data give the GP or GP nurse more insight in the health status of patients, potentially leading to better cardiovascular risk management and hypertension control. Finally, the regular ECG measurements might help in detecting occult AF in patients at risk for AF.

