3. STUDY DESIGN

In this pilot study we will evaluate the technical feasibility and clinical implementation of the Stroke Box in a small prospective cohort. After providing the Stroke Box to the patients, detailed information will be provided on the use of the Stroke Box and the patient will be helped with their first use.

The patient will use the Stroke Box to take at-home measurements for six months. Here we will be gathering data on blood pressure management, cardiac rhythm, patient engagement and have a user-based evaluation of the eHealth infrastructure. Patients will perform regular home measurements which the GP can use at the regular visits, and a nurse specialist in the LUMC will assess ECG measurements. We will keep close contact with both patient and GP to help in case of any questions. The patients will have access to the LUMC Box Support helpdesk who are an established customer service desk to help with any Box-related issues. We will ask the patients and GPs to contact us in case of any questions they might have. At the end of the pilot the user evaluation will be done through a questionnaire.

During the regular GP visits after the stroke related hospital admission, the GP and the nurse specialist will have insight in the collected data. We will evaluate the GP's experience of the data insight and technical usability using a questionnaire.

The study is estimated to take 12 months where we will have 6 months of inclusions and 6 months of follow-up.

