The LUMCcare app presents the data to the patient in an intuitive interface. The app is co-created with Pharos, the advocate group for people with low literacy, in order to ascertain the measurements are understandable for a large group of patients. The app reminds

patients to take measurements based on the protocol prescribed by the health care provider. It allows patients to fill in questionnaires at appropriate time points. The app communicates with the LUMC infrastructure according to LUMC guidelines and is approved by the LUMC security officer. As for how to use the app, patients will receive oral and written instructions. If they run into problems, a helpdesk is available, which is run by an LUMC employed technician.

Withings Health Mate app

The Withings3 Health Mate connection app requires a user specific account, that is accessed using a hospital-provided, coded username and a password. The account cannot be linked to an individual patient. This procedure complies with the LUMC requirements and has been approved by the LUMC security officer. For retrieving the data from the Withings Health Mate app, the LUMC uses an API connection, which unlocks the patient measurement data. This API has been functional for 6 years already. Authorized users can thus evaluate the e-Health measurements of the patients in the electronic patient file.

Data is securely shared with the GP office via Medical Dashboard, an dedicated information portal that allows GPs to assess specific data from the LUMC. The Medical Dashboard is operational at the LUMC for already 8 years and complies with the LUMC requirements and has been approved by the LUMC security officer. Over the course of the next years, the underlying technology will be updated to new technology, in line with the established roadmap of the It&DI department of the LUMC. This effort is currently underway and may result in selection of a novel target architecture for regional connectivity in the coming period. All efforts will be taken to ensure this study protocol can continue also during implementation of novel architectures.

In addition to this, the Health Mate app also gives the patient insight into his/her measurements. Moreover, when the Move ECG detects signs of AF during a measurement the patient is notified via the watch and the app. The patient is instructed to then take up contact with our specialist nurse.

IkOefenZelf

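### The three-day GP-contact rule for systolic pressure above 140 mmHg cannot be met on the weekly blood pressure schedule that section 8.3 sets

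*Combined protocol and SAP*

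**What the plan says.** **Schedule.** Section 8.3 states: "Patients will be asked to measure their weight and blood pressure once a week", and recommends keeping to one day and time of the week. The Summary agrees. Under the intervention it says "Patients are asked to measure the associated factors on a weekly basis", and under burden and risks "Patients are asked to measure weight, blood pressure and heart rhythm on a weekly basis". Measurement every day is requested only for heart rhythm, in patients with suspected atrial fibrillation.

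**Contact rule.** Later in section 8.3, patients with a high or fast-rising pressure are told not to call a physician straight away, in order to limit unneeded GP consultations. Instead, "the patient is instructed to only contact their GP if they record a systolic blood pressure >140 mmHg for three days in a row", or at once if a systolic reading exceeds 180 mmHg.

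**Repeats.** No section asks for a second blood pressure reading after a high one. For an inconclusive ECG, section 8.3 does: "the patient is asked to repeat the measurement the next day". According to section 6.1, the LUMCcare app reminds "patients to take measurements based on the protocol prescribed by the health care provider". The only blood pressure schedule in the documents is the weekly one.

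**Other routes to the GP.** Section 3 says: "Patients will perform regular home measurements which the GP can use at the regular visits". Section 8.3 adds that the blood pressure data "is accessible for the GP through Medical Dashboard". Where a GP does not use that system, the patient shows the app or a printout at the visit.

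**The concern.** A rule that needs readings on three consecutive days does not fit a schedule with one reading every seven days. Unless the patient decides unprompted to measure again, the lower tier of the rule has no data to act on. What remains is the instruction not to call straight away and the tier above 180 mmHg.

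The affected range is likely to occur in this cohort. Section 4.2 requires systolic pressure above 140 mmHg on two separate in-hospital measurements, and section 4.4 treats values above 140 mmHg as outside the therapeutic window. Section 1 expects generally older patients, likely with substantial physical or cognitive disability, who should not have to infer an unwritten step. Section 11.4 itself names a false sense of safety as a major potential risk.

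There is also a smaller data issue. If some patients read the rule as a request for daily repeats and others do not, the number of readings per patient will depend on interpretation as well as on adherence. Section 10.1 summarises measurements per week and change in blood pressure as input to the future trial's sample size.

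**Working it through.** The documents give no figure to reproduce here; the check sets the schedule against the rule.

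**Inputs from the documents.** One blood pressure reading per week (section 8.3, Summary); six months of follow-up (section 3), taken as 26 weeks or 182 days; contact if systolic pressure is above 140 mmHg on three consecutive days, or immediately above 180 mmHg (section 8.3).

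**As written.**
- Reading days are 0, 7, 14, ..., 175, which gives 26 readings with a gap of 7 days.
- Runs of three consecutive days: 0. Runs of two consecutive days: 0.
- If the patient takes one reading on any day of each calendar week, runs of three are still 0, because three consecutive days span at most two calendar weeks and so contain at most two readings.
- The probability of meeting the lower tier is therefore 0 at any sustained systolic pressure above 140 and up to 180 mmHg.

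**With two next-day repeats after each high weekly reading.**
- Each of the 26 weekly readings can start a qualifying run, against 0 now.
- Readings per week are 1 to 3, so the total is 26 to at most 26 × 3 = 78.
- The rule can be met 2 days after the first high value.

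**With three consecutive weekly readings instead.** The rule can be met after 2 × 7 = 14 days, with no extra readings.

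**Illustration of how the repeat rule would behave.** This rests on assumptions that are not in the documents: independent, normally distributed readings, a within-patient SD of 8 to 12 mmHg, and full compliance with repeating and calling. Let p be the probability that one reading exceeds 140. The rule is met in a given week with probability p³, and at least once in k weeks with probability 1 − (1 − p³)^k.

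| True home systolic (mmHg) | SD | p | p³ | k | Contact within k weeks |
|---|---|---|---|---|---|
| 150 | 8 | 0.894 | 0.715 | 4 | 99% |
| 150 | 12 | 0.798 | 0.508 | 4 | 94% |
| 142 | 8 | 0.599 | 0.215 | 4 | 62% |
| 142 | 12 | 0.566 | 0.181 | 4 | 55% |
| 130 | 8 | 0.106 | 0.0012 | 26 | 3% |
| 130 | 12 | 0.202 | 0.0083 | 26 | 19% |

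Under these assumptions, repeats would bring most patients at 150 mmHg to the GP within a month. Few patients at 130 mmHg would call during the whole follow-up. Just above the threshold, detection within four weeks is clearly lower.

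**The case against.** The strongest reply is that the rule implies the repeats. It is addressed to someone who has just seen a high value and has the cuff at home; told to call only after three high days, that person would naturally measure on the next two. Weekly measurement is a request, its day and time are only recommended, and nothing caps the number of readings. On this view the zero follows from assuming that nobody re-measures. Part of this stands: extra readings are not forbidden, and repeats may well have been intended. But section 8.3 spells out a repeat for the ECG and none for blood pressure, and the app reminders follow the prescribed schedule.

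Second, the patient information form, the device guides and the oral instructions are not among the documents, so a repeat instruction there cannot be excluded. That is a real limit. It does not repair the protocol text from which those materials should be drawn.

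Third, the consequence is bounded. The sponsor meant to limit calls, the tier above 180 mmHg works, and usual care continues. Section 3 gives the GP and the nurse specialist insight into the data around regular GP visits and promises close contact for questions. This also stands, but no section sets a schedule for actively reviewing blood pressure values between visits.

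Finally, the illustrative percentages describe the remedy and not the defect, and they depend on the assumed SD and on independence between days. They carry no weight in the conclusion. Likewise, inflated reading counts in section 10.1 arise only where repeats are actually taken, so they are a matter for the fix.

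**Conclusion.** The concern holds. Followed exactly, section 8.3 gives a contact rule that cannot be met for systolic pressure above 140 and up to 180 mmHg: 26 scheduled readings and no run of three consecutive days. The result depends on one condition, that the patient measures only as scheduled, and on nothing outside the documents.

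For such a patient, sustained values in this range reach the GP only if the GP opens Medical Dashboard or at a regular visit. For GPs without that system, the patient must show the values at the visit. This is a stated safety rule that fails on the written schedule; it is not a loss of all follow-up. It should be corrected, because the cohort is enrolled for pressures in or above this range and the correction is small.

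**What to change.** Add to section 8.3, the patient instructions and the app reminders: after any scheduled systolic reading above 140 mmHg, measure again on each of the next two days, and contact the GP if all three readings exceed 140 mmHg. Leave the rule above 180 mmHg as it is. This keeps the sponsor's three-day filter on GP consultations.

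An alternative is to restate the rule as three consecutive weekly readings above 140 mmHg. That needs no extra readings, but the earliest contact is then 14 days after the first high value instead of 2.

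If repeats are added, flag them in the data and specify in section 10.1 that change in blood pressure and mean measurements per week use the scheduled weekly readings, with triggered readings reported separately. Otherwise a patient with persistently high values could show up to 3.0 readings per week against 1.0 for another patient with the same adherence.

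The cost is wording in three places, a data flag, at most two extra home readings in a week with a high value, and possibly some additional GP contacts, which the current rule was written to limit. No new staff or devices are needed.
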